### Power and Significance

The margin for this study is 15% which means that RARC would be considered inferior if the true progression free survival at two years was more than 15% lower than the progression-free survival at two years in the ORC arm. A total of 288 evaluable patients (144 patients per arm) yield a study with 80% power and a two-sided significance level, alpha, of 5% to correctly reject the null-hypothesis of unacceptable inferiority. These calculations are based on the assumption that progression-free survival at two years in the patients receiving ORC is approximately 71% and that the rate of progressions at two years is binomially distributed. Evaluable patients are defined as eligible patients who have no major protocol deviations and have 90-day post-surgery follow-up data. Major protocol deviations will be recorded for patients with no surgery given, where surgery was started correctly but discontinued before cystectomy was completed; or where the patient received a surgery type different from their randomization assignment for any reason. In addition, a major protocol deviation will be recorded if the surgery begins as assigned, but the robotic procedure is aborted and an open procedure is required to complete the operation.

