### **Analysis of Primary Endpoint**

A one-sided mantel-Haenszel test with half the alpha (0.025) will be used for testing the primary non-inferiority hypothesis that compares progression free survival at two years in the two treatment arms.

In superiority trials the intent to treat (ITT) population is widely accepted as the analysis population for the primary endpoint as it gives the most conservative result of such a study. In contrast, for non-inferiority trials the inclusion of ineligible or untreated patients or the lack of adherence to the assigned treatment is expected to increase the noise of the study and make the two treatment arms look more alike, thus the overall results of the study less conservative. Thus we will use the per-protocol (PP) population as the analysis population for the primary endpoint. We will also perform a sensitivity analysis of the primary endpoint using the ITT population. These two analysis populations are defined below. The design and analysis of this trial are based on the SWOG standards for noninferiority trials, which are detailed the chapter 12 in the Handbook for Statistics in Clinical Oncology, second edition, Chapman & Hall 2006.

Serum hemoglobin, serum creatinine and serum albumin levels will be taken at baseline and at a variety of time points post-surgery throughout the study. Linear mixed effects will be used to compare these blood levels and their changes over time between the two treatment groups.

QOL outcomes will be measured at baseline and in the post-operative period at 3 and 6 months using the Functional Assessment of Cancer Therapy – Vanderbilt Cystectomy Index (FACT-VCI) as well as the Short Form 8 (SF-8) Questionnaires. Simple descriptive statistics, such as mean and standard deviation, will be used to summarize the FACT-VCI and the SF-8 scores at each time point and for each treatment group. A multivariate linear mixed effects model will then be fitted to each score in this repeated measures design. The main effect will be visit (at baseline, 3 and 6 months) and will be treated as a categorical variable to accommodate for the non-linear trends. If the exact time corresponding to a particular visit differs significantly between patients a variable

representing the deviation from the visit-specific mean time will be added to the model. Standard diagnostic tools will be used to assess model fit.

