**Secondary Endpoints**

We will determine whether RARC is superior to ORC in terms of blood loss. More specifically, the overall blood loss due to surgery will be compared between the two treatment arms. In the ORC group the average blood loss is 575 ml . 288 patients yield 90% power to detect a difference of blood loss between the two treatment groups of 20%. These calculations are based on the assumption that the amount of blood loss is normally distributed, that the average blood loss in the open surgery group is 575ml, and that the standard deviation of blood loss is 300ml. A one-sided significance level of 0.025 was used.

We will determine whether RARC is superior to ORC in terms of transfusion rates. The transfusion rates (proportion of patients requiring blood transfusions) will be compared between the two treatment arms. The transfusion rate for ORC is approximately 75%(from Table 2, unpublished). 288 patients yield 92% power and a one-sided significance level of 0.025 to detect a difference of transfusion rates between arms of at least 20%. These calculations are based on the assumption that the transfusion rate is binomially distributed.

*Table 2 (Preliminary Data from University of Texas Health Sciences Center, San Antonio)*

|  | ORC (n=12)  | RARC(n=12)      | p-value |
|--|-------------|-----------------|---------|
| Median (IQR) Units of Blood Given | 2.5 (1-5)   | 0 (0-3)         | 0.082   |
| Transfusion given (%)             | 9/12 (75%)  | 4/12 (33%)      | 0.041   |
| Median (IQR) LOS (days)           | 6.5 (6-8.5) | 6.5 (5-9.5)     | 0.554   |
| LOS (5 days or less)              | 0/12 (0%)   | 4/12 (33.3%)    | 0.028   |
| Median No. LNs (IQR)              | 19 (6-27)   | 10.5 (8.5-17.5) | 0.30    |
| Positive margin                   | 3/12 (25%)  | 0/12 (0%)       | 0.064   |

*All positive margins in the ORC group had pT4 disease.*

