Hand Grip Strength at 3 months after surgery will be measured as a surrogate for recovery after surgery. It was found that only 39% of patients recovered at three months after a major abdominal surgery as measured by the Hand Grip Strength. We will compare the proportion of patients recovered as measured by Hand Grip Strength between the two treatment arms. We hypothesize that 20% more patients will have recovered three months after surgery in the RARC arm compared to the ORC arm. A total of 288 patients yield 91% power and a one-sided significance level of 0.025 to detect a difference between arms of at least 20%. These calculations are based on the assumption that Hand Grip Strength at three months is binomially distributed. Surgical margin as a measure for local cancer control will be measured as positive or negative for each patient and compared between arms using a Fisher's exact test. The number of nodes resected in each arm will be compared using a t-test.

Progression-free and overall survival will be evaluated using the method of Kaplan Meyer and comparisons between arms will be made using the stratified log-rank test.

All efficacy and QL endpoints will be assessed using the PP population.

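### Four powered tests that RARC is better appear to be planned in the per-protocol population only, which probably drops robotic-to-open conversions from one arm, with no by-randomized-arm analysis as a check

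*Combined protocol and SAP*

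**What the plan says.** **The four tests.** Section 5, Secondary Endpoints, says of blood loss "We will determine whether RARC is superior to ORC in terms of blood loss" and of transfusion "We will determine whether RARC is superior to ORC in terms of transfusion rates". It words hospital stay in the same way. For grip strength it hypothesizes 20% more patients recovered at three months under RARC. Each test has its own power figure (90%, 92%, 97% and 91%), a one-sided level of 0.025 and 288 patients.

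**Their population.** No population is named test by test. The section closes with "All efficacy and QL endpoints will be assessed using the PP population", and the PP definition under Analysis Populations repeats the rule. Efficacy is not defined. ITT has one role, under Analysis of Primary Endpoint: "We will also perform a sensitivity analysis of the primary endpoint using the ITT population". The ITT definition confirms this. No all-operated or as-treated set is defined.

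**Who is in PP.** Analysis Populations defines PP as eligible patients who had the operation allocated to them. Power and Significance defines a different set: "Evaluable patients are defined as eligible patients who have no major protocol deviations and have 90-day post-surgery follow-up data". Its major deviations include cases "where the patient received a surgery type different from their randomization assignment for any reason" and, as a separate item, a deviation recorded "if the surgery begins as assigned, but the robotic procedure is aborted and an open procedure is required to complete the operation".

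**The concern.** The plan defends PP on the ground that ineligible, untreated or non-adherent patients make the arms look alike, which is anti-conservative for non-inferiority. In a test that RARC is better, that dilution works against the claim, so the argument gives no reason to leave those patients out. No other reason is offered.

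PP also selects on events after randomization. One of them, conversion, can arise only in a patient allocated to RARC whose operation began robotically. If those patients are removed and fare worse than the rest of their arm, RARC is compared with ORC after shedding some of its worst outcomes, while ORC sheds none for a matching reason.

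The protocol's Background warns that RARC's apparently better recovery may reflect patient selection. A superiority claim resting on PP alone would be open to the same criticism. The primary test uses the same PP set, but it at least has a planned ITT analysis beside it.

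**Working it through.** **1. The plan's own power figures.** Inputs from Secondary Endpoints: ORC mean blood loss 575 ml, SD 300 ml, 20% difference, one-sided 0.025, 288 patients (144 per arm).

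- Blood loss: difference = 0.20 × 575 = 115 ml. SE = 300 × √(2/144) = 35.4 ml. Power = Φ(115/35.4 − 1.96) = 90.2% (plan: 90%).
- Binary endpoints, with continuity correction: power = Φ{[|p1 − p2| − 1/n − 1.96√(2p̄(1 − p̄)/n)] / √[(p1(1 − p1) + p2(1 − p2))/n]}, n = 144. Transfusion 75% v 55%: 93.4% (plan: 92%). Stay 87% v 67%: 97.7% (plan: 97%). Grip 39% v 59%: 91.1% (plan: 91%).

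The figures agree within about 1.5 points. All four rest on 288, the evaluable count, which excludes conversions.

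**2. The two definitions side by side.**

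| Patient | Evaluable (Power and Significance) | PP (Analysis Populations) |
|---|---|---|
| Never operated | out | out |
| Had the other operation | out | out |
| Robotic converted to open | out | not stated |
| Stopped before cystectomy completed | out | not stated |
| No 90-day data | out | no such requirement |

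Conversion is listed apart from receiving a different operation, so the PP wording alone does not settle it. The reuse of 288 points towards exclusion.

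**3. What excluding conversions could do to blood loss.** Assumptions, none from the documents: conversions are excluded, there is no true difference as randomized, 144 per arm are analysed, and the SD stays at 300 ml. Let c be the converted share of the RARC arm and e their excess over the as-randomized RARC mean m. If x is the mean of those left, m = (1 − c)x + c(m + e), so x = m − ce/(1 − c). The bias towards RARC is ce/(1 − c), and type I error = 1 − Φ(1.96 − bias/35.4).

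For c = 5%, e = 300 ml: bias = 15/0.95 = 15.8 ml, and 1 − Φ(1.96 − 0.447) = 6.5%.

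| Excess e | c = 2% | c = 5% | c = 10% |
|---|---|---|---|
| −150 ml | 2.0% | 1.5% | 0.8% |
| 0 | 2.5% | 2.5% | 2.5% |
| +150 ml | 3.1% | 4.1% | 6.8% |
| +300 ml | 3.7% | 6.5% | 15.5% |

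**4. The binary endpoints at c = 5%.** With a common rate p, and rate q in converted patients, the PP RARC rate is (p − cq)/(1 − c). Pooled-variance test, 144 per arm.

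- Transfusion, p = 75%: if all converted patients are transfused the rate is 73.7% and type I error 4.4%; if 60% are, 1.7%.
- Grip, p = 39%: if none recover the rate is 41.1% and type I error 5.4%; if 50% recover, 2.0%.
- Stay: at the plan's 100% ORC rate and no true difference, nothing shifts. At an assumed common rate of 90%, with all converted patients staying longer, 3.5%.

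If conversions stay in PP, every figure in steps 3 and 4 is 2.5%.

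**5. Blood-loss power when conversions are kept.** Power = Φ(d/(300√(2/n)) − 1.96), with n = 175 per arm, or 158 after the plan's 10% drop-out (350 × 0.9 / 2 = 157.5).

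- If 115 ml is the as-randomized effect: 93% (n = 158) to 95% (n = 175).
- If 115 ml holds only in unconverted patients and e = 300 ml: d = 115 − 300c/(1 − c) = 109 / 99 / 82 ml at 2 / 5 / 10% conversion. Power is 90–92 / 84–87 / 68–72%.

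**The case against.** **The harm is assumed.** This stands. No conversion rate or outcome is given. The 15.5% needs 10% conversions and a 300 ml excess together, and some cases fall below 2.5%. The eligibility criteria exclude patients in whom a robotic approach or pneumoperitoneum would be unsafe, and surgeons need at least 10 procedures in the past year. Both plausibly keep conversions low, though neither is quantified.

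**The tests may not be on PP at all.** The aims list blood loss, transfusion and stay as perioperative measures, and efficacy is undefined. This also stands, but it does not close the gap: any test outside the PP sentence then has no stated population.

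**The plan contradicts itself.** A reader might infer this from "In superiority trials the intent to treat (ITT) population is widely accepted as the analysis population for the primary endpoint". That sentence is worded for primary endpoints and these four are secondary, so the documents show a gap, not a contradiction. Nor does PP regroup patients by the operation received: anyone in PP had the assigned operation. What is missing is an analysis that keeps the excluded patients.

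**An all-operated analysis also selects after randomization.** True: surgery may follow randomization by up to 60 days. But blood loss, transfusion and stay have no value without an operation, and conversion is no longer a ground for exclusion. Reporting never-operated patients by arm shows what selection remains.

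**Conclusion.** The gap holds. On the natural reading, four powered tests that RARC is better rest on PP alone, for a reason that applies only to non-inferiority, with no planned analysis that keeps excluded patients. Whether converted patients are in PP is unstated, and their exclusion is the more likely reading.

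A reader might go further and infer that these comparisons are biased towards RARC. The documents do not support that. The bias is zero if conversions stay in PP or do as well as the rest of their arm, and it reverses if they do better. The error rates above are illustrations over assumed conversion shares and outcomes, not estimates for this trial.

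These are secondary endpoints, so the point does not undermine the primary design. It should still be fixed before comparative data are seen, because it bears on any claim of RARC's advantage and costs little to close.

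**What to change.** 1. **Secondary Endpoints and Analysis Populations.** State that the four superiority endpoints are analysed by randomized arm, with conversions and crossovers kept in their assigned arm, and PP as supportive. Use all randomized patients where the endpoint exists. For blood loss, transfusion and stay, use all operated patients, and report by arm the number of never-operated patients and the reasons. Handling of missing grip values is a separate matter.
2. **Other secondary comparisons under the same PP sentence** (QL scores, margins, node counts, the PFS and OS log-rank tests). Add the same by-randomized-arm analysis as a sensitivity analysis.
3. **Power and Significance against the PP definition.** Before comparative data are seen, reconcile the two on whether conversions and the other major deviations are in PP. This also fixes the primary test's population.

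Keep PP as primary, with its ITT sensitivity analysis, for the non-inferiority test.

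**Cost.** No new data collection: operative, hospital-stay and grip data are already collected. A few more analyses are run. The apparent RARC benefit may shrink, with the effect on blood-loss power shown in step 5 of the working.

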### **Analysis Populations:**

#### **Per Protocol Population (PP Population):**

The per-protocol population includes all patients who have met inclusion/exclusion criteria and received the surgery to which they were randomized. This is the primary efficacy population. All efficacy and QL endpoints will be assessed using this population.

## **Intent-to-Treat Population (ITT Population):**

The ITT population includes all patients who have been randomized to the trial. Patients are assigned to treatment arms based on what they are “randomized” to receive. This is the sensitivity analysis population of the primary efficacy endpoint.

## **6. HUMAN SUBJECTS**

### **Compensation**

There will be no compensation provided to subjects for participating in the study.

### **Risks to Subjects**

The only research related risks to subjects are the potential loss of PHI and potential mental distress during conduct of questionnaires. Measures to maintain confidentiality are being employed. For a detailed description, please see the section titled “Confidentiality.” Should patients express discomfort during questionnaires or other assessments, they will first be allowed to take a break from questioning. If distress persists, the session will be terminated. Participants may refuse to answer questions which cause them discomfort rather than being withdrawn from the study.

### **Special Precautions**

Subject data will be examined at each follow up visit and subjects queried for adverse events (AE) defined as complications related to the robotic/open cystectomy and/or study procedures. An AE or complication is the appearance of undesirable sign(s), symptom(s), or medical condition(s) occurring after a participant signs the informed consent and considered to be related to the robotic/open cystectomy and/or study procedure. A serious adverse event is any untoward medical occurrence that:

1. Is fatal or life-threatening
2. Requires hospitalization or prolongation of existing hospitalization
3. Results in disability/incapacity
4. Is medically significant in that it may jeopardize the patient and may require medical or surgical intervention to prevent one of the outcomes listed above.

All AEs or complications will be graded for severity according to the modified Clavien grading system. All adverse events will be reported to the IRB at the time of annual review and to the DSMC as described below.

The investigator is obligated to assess the relationship between any study-related procedure and the occurrence of each SAE. The investigator will use clinical judgment to determine the relationship. Alternative causes, such as natural history of the underlying diseases, concomitant therapy, other risk factors, and the temporal

relationship of the event to any study-related procedure will be considered and investigated.

Even in situations when an SAE has occurred and the investigator has incomplete information to include in the initial SAE report, the investigator will make an assessment of causality for every event prior to reporting it. The investigator may change his opinion of causality in light of follow-up information and amend the SAE case report form and report accordingly.

SAEs meeting the IRB definition of Unanticipated Problems Involving Risk to Subjects or others (UPIRSO) will be reported to the IRB within 7 days, and within 48 hours if life-threatening or fatal or will follow the guidelines as required by the local IRBs.

All SAEs will also be reported to the coordinating center office of [name] at the University of Miami. After completion of review by [name], SAEs will be summarized and communicated across sites via the posting to the study website at <https://prodq.crab.org/[name]/Login.aspx>.

The data will be reviewed on a biweekly basis by the investigators to ensure quality control and safety. During the study when there is a safety evaluation, the investigator and/or research staff will be responsible for detecting, documenting and reporting any adverse events or serious adverse events to the IRB.

### **Subject Completion and Withdrawal**

A subject will be considered completed when he/she has completed all follow-up visits up to the 24 month evaluation. A subject may discontinue participation in this study at any time at the investigator's discretion or at the request of the subject. The reason for study withdrawal will be documented in the study related source documentation.

### **Alternative Treatments**

Subjects who are eligible for the proposed study will be randomized to receive either open or robotic-assisted cystectomy. The alternative to participating in this study would be for a subject to choose which surgical technique will be used rather than being randomized to one or the other.

### **Confidentiality**

Maintaining confidentiality of patient-specific information will be top priority throughout all phases of the study. Patient data (PHI) will be compiled in a database and de-identified upon completion of analysis. Cases in the database will be identified by initials, patient identification number, the year of patient's birth, and the date of surgery. The database will not include information which can be identifiable with the link (or key). All electronic data will be stored in a password protected database in accordance with institutional computer-security policies. The identification number is actually a research record number that cannot be linked to the subject except by a key. This key will be maintained securely by the Principal Investigator. The data will be stored and maintained by the CRAB informatics core facility.

## **Data Safety Monitoring Committee**

A Data and Safety Monitoring Board will oversee the conduct of the study. The Board consists of 5 voting, independent members: 1 surgeon, 1 medical oncologist, 1 CCRA/RN, 1 biostatistician, and 1 lay person. Non-voting members include support staff from Cancer Research And Biostatistics (who will prepare the DSMC reports), and project faculty (Principal Investigators) as appropriate. DSMC members receive database summaries from CRAB, including adverse events and post surgical complications reports, serious adverse event summaries, and other pertinent patient/treatment summary information. Meetings occur every six months, convened via teleconference. The DSMC is responsible for decisions regarding possible termination and/or early reporting of the study.

## Appendix A: ECOGa Performance Status Scale

| Grade | Status  |
|-------|---|
| 0     | Fully active, able to carry on all pre-disease performance without restriction  |
| 1     | Restricted in physically strenuous activity but ambulatory and able to carry out work of a light or sedentary nature, eg, light house work, office work |
| 2     | Ambulatory and capable of all selfcare but unable to carry out any work activities. Up and about more than 50% of waking hours                          |
| 3     | Capable of only limited selfcare, confined to bed or chair more than 50% of waking hours  |
| 4     | Completely disabled. Cannot carry on any selfcare. Totally confined to bed or chair   |
| 5     | Dead  |

a As published in *Am J Clin Oncol (CCT)*. 1982;5:649-655.

## **APPENDIX B: Data Collection Forms**

See Mock-ups of CRAB eCRF webpages
